5 STUDY PROCEDURES

Following IRB approval and informed consent, eligible participants randomized to either the experimental ($n = 7$) or control group ($n = 7$) and scheduled for baseline data collection. Laboratory, demographic, and anthropometric assessments were completed UAB's Clinical Research Unit (CRU). Baseline data: demographic questionnaire, oral glucose tolerance test (OGTT), inflammatory assays and lipid panel as well as an anthropometric evaluation. Even though all snacks and meals for the KD group provided, KD group participants also provided nutritional counseling specific to the KD as well as provided with handouts. Food selected from an 8-day menu. Meals matched for energy content to maintain current energy balance (eucaloric) consisting of < 50 grams CHO/day. Daily CHO intake primarily derived from fresh vegetables.

After laboratory assay and body composition assessments collected, questionnaires and cognitive testing in a private conference room away from outside distractions completed. Delivery of meals/snacks (week 1) to begin the week following baseline data collection.

Food delivery via courier on the same day of the week across the study. All frozen/refrigerated items delivered in a commercial grade cooler. All items clearly labeled with easy-to-understand preparation instructions.

Data Collection

Data collection in the UAB Clinical Research Unit after a 12-hour fast collected by registered nurses well-versed in research methodology. Data collection described below. **Data collection collected at baseline**

and week 12 unless otherwise stated. **NOTE: Cognitive assessments completed at baseline, week 12, and week 18.**

Demographics (baseline only): Age, education, gender, marital/partner status, employment status/disability eligibility, SES (Medicaid, food stamps, public housing eligibility), years since HIV diagnosis (baseline only).

[figure not shown]
Anthropometrics: Height, weight, BMI, waist and hip circumference (baseline/week 12). Height (nearest 0.1 cm), waist circumference (nearest 0.1 cm), and hip circumference (nearest 0.1 cm) measured with Gulick tape measure. Weight (nearest .01 kg) assessed using a Tanita body composition analyzer BC418, Tanita Corp of America, Arlington Heights, IL. BMI calculated.²³ Waist circumference measured at the umbilicus at end of inspiration. Hip measures evaluated at widest hip portion.

Oral Glucose Tolerance Test (OGTT): 75 g at baseline (time 0). At ~7 am, after a 12-h fast, a flexible intravenous catheter will be placed in an antecubital space. Blood samples will be collected at times 0, 10, 20, 30, 60, 90, and 120 minutes. OGTT performed at baseline. Fasting glucose, insulin, and c-peptide to be assessed at week 12.

Lipids: Total, high density cholesterol (HDL) and triglycerides were measured using SIRRUS analyzer and low density lipoprotein were calculated using the method of Friedewald.³⁰

Inflammation Markers: Assessed by immunoassay in fasting morning sera before and after the intervention. High-sensitivity C-reactive protein (CRP), TNF- α and IFN γ , IL-1B, IL-6, IL-8, and IL-12p70

Cognitive Battery Domain

Cognitive Measures

[figure not shown]

[figure not shown]
Speed of Processing

WAIS-III Digit Symbol measures visuospatial tracking, attention, and speed of processing. Participants are presented with a key which has numbers paired with a unique symbol. They are given rows of numbers with blank spaces underneath them. The task is to use the key to fill in the blank spaces with the symbol that corresponds to that number. Scores are calculated by the number of squares filled in correctly.

WAIS-III Symbol Search is similar to the Digit Symbol Test. Participants are given rows of symbols and must use the key to write the corresponding number (1-9) in the blank under the symbol.

Trails Making Test A – This measure of motor speed and speed of processing is very reliable ($r = 0.80 - 0.90$) Twenty-five circles numbered 1 to 25 are located randomly on the page. Participants instructed to connect the dots sequentially (1-2-3-4). The score is determined by the time to complete.

[figure not shown]

Attention

WAIS-III
Digit Span – A measure of attention and concentration. Participants must recall blocks of sequenced numbers (1 through 9) presented to them; the length of the blocks are small at first and slowly build making it more difficult to attend. Digits are to be immediately recalled forward (e.g., 1..2..3) and backward (e.g., 3..2..1).

[figure not shown]

Verbal

[figure not shown]
Hopkins

Verbal Learning Test-Revised (HVLTR) Trials 1-3 – A test of verbal recall and consists of 12 words, four

[figure not shown]

from each of three semantic categories. The total recall is used in analyses, but true-positive recognitions and false-positive errors can be used.

**Learning/
Memory**

Verbal Learning Test-Revised Delay – A test of delayed verbal memory, it is administered 25 min after the

[figure not shown]

HVLT-R Trials 1-3 to measure long-term verbal memory. Scores equal the sum of the words correctly recalled.

**Verbal
Memory**

Executive

Trails

[figure not shown]
Making Test B –Participants are scored on the time it takes to connect 25 circles in an ascending pattern that

Function

requires alternation between numbers (1 to 13) and letters (A to L) (i.e., 1-A-2-B-3-C, etc.). Thus, a good performance on this test requires mental alertness and concentrated attention as well as the ability to shift between numbers and letters (i.e., cognitive flexibility).

Stroop Interference – A measure of selective attention and executive function. Participants are presented with names of colors printed in a conflicting colored ink. First, they will read the printed color name. Second, they will name the color of the ink in which the word is printed. The time to complete each task is recorded. The difference between the times is calculated. The greater the difference between the times for task 1 and 2, the poorer their executive functioning.

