2. STUDY OBJECTIVES

In medically stable, older (> 50 years) HIV patients with cognitive impairment, this study will:
Test the feasibility of recruitment, retention, and adherence to a ketogenic diet versus patient choice diet (PCD) intervention.

2.1 Primary: Compare the impact of a 12-week KD versus PCD on:

1. 2.1.1 Cognitive function (*at 12 weeks*).
 2. 2.1.2 Inflammation (*at 12 weeks*).
 3. 2.1.3 Cardiometabolic profile (*at 12 weeks*).
 4. 2.1.4 Persistence of cognitive effects (*at 18 weeks*).
3. STUDY DESIGN: Randomized, 2-group pre/post design. Participants randomized using permuted block randomization using an algorithm developed by the UAB Center for Clinical and Translational Science Biostatistics, Epidemiology, & Research Design (BERD) team. Due to the nature of the intervention (diet) it isn't possible for participants/study personnel to be blinded.

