6. STATISTICAL PLAN

Sample Size. Feasibility and preliminary data for effect size estimation is the primary purpose of this pilot

study (hypothesis generating).

Descriptive analyses.

Demographic, Anthropometric and Baseline Characteristics: Demographic data (i.e., age, education, gender, marital/partner status, employment status, and years since HIV diagnosis) were evaluated using frequencies and reported for each group. Ratio/interval data (i.e., anthropometrics (i.e., height, weight, BMI, waist and hip circumference, cognitive performance by instrument; inflammatory markers (CRP, TNF-a, IFNy, IL-1B, IL-6, IL-8, and IL-12p70); cardiometabolic factors (OGTT, glucose, C-peptide, and insulin) reported via mean/SD at baseline by group. Between-group t-tests will explore group differences at baseline.

Primary analysis: All the primary outcomes (impairment score, inflammatory markers and cardiometabolic factors) will be examined by an analysis of covariance (ANCOVA) including the change from baseline to completion of diet treatment as dependent variable, study group as independent variable, and baseline measures as a covariate, to evaluate the effects of a 12 week KD versus PCD. The lasting cognitive effects of a 12-week KD versus PCD six weeks post intervention completion was determined by an ANCOVA including the change of impairment score from 12 week to 18 week as dependent variable, study group as independent variable, and impairment score at 12 weeks as a covariate.

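### Section 5 randomises before the baseline visit in an unblinded trial with no rule withholding allocation, so the baseline cognitive score used in the 12-week ANCOVA may not be a pre-allocation measure.

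*Combined protocol and SAP*

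**What the plan says.** **Order.** Section 5 places IRB approval and consent first, after which it has "eligible participants randomized to either the experimental ($n = 7$) or control group ($n = 7$) and scheduled for baseline data collection". The cognitive tests belong to that later visit. Once the laboratory and body composition work is done, it has "questionnaires and cognitive testing in a private conference room away from outside distractions completed".

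**Blinding.** Section 3 says that because the intervention is a diet "it isn't possible for participants/study personnel to be blinded". It makes no exception for whoever gives the cognitive tests.

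**Disclosure.** The document does not say when participants or testers learn the assignment. What Section 5 delays until after baseline is the food: "Delivery of meals/snacks (week 1) to begin the week following baseline data collection". Counselling has no stated time: "KD group participants also provided nutritional counseling specific to the KD as well as provided with handouts".

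**Use of baseline.** Section 6 models the change from baseline to the end of the diet, with "study group as independent variable, and baseline measures as a covariate". The persistence analysis instead models the change from week 12 to week 18 and adjusts for the week-12 score.

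**The concern.** A baseline covariate is safe to adjust for in a randomised comparison because allocation cannot have influenced it. That guarantee is lost if the value is collected after the participant or tester knows the arm. The cognitive battery is the part most open to such influence. It consists of recall and speeded tasks carried out with an examiner; for the Stroop test, for example, "The time to complete each task is recorded". Effort, expectation or the manner of testing could differ between a participant who has just been assigned provided ketogenic (KD) meals and one assigned to patient choice (PCD).

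Cognitive function is the first comparison listed in Section 2.1, and Section 6 gives effect-size estimation as part of the pilot's main purpose. A baseline shifted by known allocation would pass into that estimate. The data could not separate it from a similar influence at week 12.

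The blood outcomes are less exposed. The inflammatory markers are "Assessed by immunoassay in fasting morning sera before and after the intervention", so knowing the arm would matter only if a participant changed diet before the visit.

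**Working it through.** The plan gives no alpha, power, effect size or SD, so it has no figure of its own to reproduce. The finding rests on the text; the arithmetic only shows how a shift would travel.

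**Step 1: the text.**
- Randomisation precedes the baseline visit (Section 5).
- Participants and personnel are not blinded (Section 3).
- No section describes withholding the assignment or a blinded tester.
- The TICS-M eligibility screen (Section 4) comes before randomisation, but Section 6 does not name it as the ANCOVA baseline.
- The impairment score in Section 6 is not defined. The Section 5 battery is the only cognitive data collected at baseline, so the link is a reasonable inference.

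**Step 2: how a baseline shift enters the estimate.** Let Y be the week-12 score, X the baseline score and b the slope of Y on X. In the ANCOVA on change the coefficient of X is b − 1, so the group effect is

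(difference in Y − difference in X) − (b − 1) × difference in X = difference in Y − b × difference in X.

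If known allocation shifts the between-arm difference by s at baseline and by f at week 12, then **bias = f − b·s**. Using change as the outcome does not alter this.

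**Step 3: illustration.** The values of s, f and b are assumed. None is in the document, and s may be zero. Units are SDs. The standard error uses 7 per arm, with 2n − 4 = 10 in the covariate term: SE = √[(2/7)(1 − b²)(1 + 1/10)].

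| b | SE | bias size, f = 0, s = 0.2 | bias size, f = 0, s = 0.4 | bias, f = s = 0.4, as written | bias, f = 0.4, baseline protected |
|---|---|---|---|---|---|
| 0.5 | 0.486 | 0.10 | 0.20 | 0.20 | 0.40 |
| 0.7 | 0.400 | 0.14 | 0.28 | 0.12 | 0.40 |
| 0.9 | 0.244 | 0.18 | 0.36 | 0.04 | 0.40 |

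With s = f = 0 the bias is zero. Simulation of the planned model (100,000 trials per setting) agreed. With f = 0 and s = 0.4 the mean bias was −0.201, −0.280 and −0.360, with SDs 0.497, 0.410 and 0.251. Bias over SD was therefore 0.40, 0.68 and 1.43.

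**Step 4: when does protecting baseline lower total bias?** It replaces f − b·s by f. This is smaller in size when f² < (f − b·s)², that is when f/s < b/2: below 0.25, 0.35 and 0.45 for b = 0.5, 0.7 and 0.9, including any case where f and s have opposite signs. Above that ratio the total bias rises.

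**Step 5: timing labels.** Section 5 uses week 1 for the first food delivery, in the week after baseline. The note on testing fatigue at the end of Section 7 places data collection with the glucose tolerance test in weeks 1 and 12, although Section 5 schedules that test at baseline. The labels conflict. That all baseline measures precede study food therefore rests on the Section 5 wording.

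**The case against.** The strongest objection is that the change may not reduce bias. Week 12 is unblinded as the plan stands, after 12 weeks of living with the allocation, so nothing supports assuming that f is small beside s. If the two shifts are equal, Step 3 shows more total bias with a protected baseline than without. This stands to the extent that lower total bias is not shown. It does not justify the present order, because hoping that two unknown distortions cancel is not a design. With a protected baseline one unknown remains, and it can be stated openly. The objection also shows that the week-12 assessment is the more certain exposure, and that Section 3's stated reason, the nature of the diet, does not obviously rule out a blinded tester.

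A second objection is that the harm is conditional throughout: disclosure before baseline, a response to it, and a different response by arm. This is correct and limits the severity. A reader might infer that baseline was in fact measured with the arm known, or that the 12-week result is biased. The document supports neither; it shows a sequence and a missing safeguard.

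A third is that this is a pilot of 14 described as hypothesis generating. A reader of Step 3 might infer that the bias exceeds chance error. It does so only in the most extreme assumed setting, at 1.4 standard errors, and elsewhere it is smaller. The ranges show scale and are not evidence of harm.

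**Conclusion.** The point holds as a gap in the stated sequence. As written, the plan does not ensure that the baseline cognitive score precedes knowledge of allocation, and that score appears to enter the 12-week ANCOVA twice. Severity is minor to moderate. The order, the lack of blinding and the absence of a withholding rule can be read directly from the document. Actual early disclosure, any resulting shift, and its size and direction cannot. The link from the battery to the impairment score is inferred.

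The point does not reach the week-18 analysis, which does not use this baseline. A reader might extend it to the inflammatory and cardiometabolic outcomes, but these are only weakly exposed.

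**What to change.** Rewrite Section 5 in this order: consent and eligibility; complete baseline visit (bloods, anthropometrics, questionnaires, cognitive tests); randomisation and disclosure of the arm; then KD counselling and food delivery. Alternatively, keep the order and state that the assignment is withheld from participants and testers until baseline is complete.

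In the same edit:
- define the impairment score and say which tests form it;
- reconcile the week 1 labels in Sections 5 and 7;
- state the unblinded week-12 cognitive assessment as a limitation, since neither option removes it, and say whether a blinded tester was considered.

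The cost is wording and a later release of each allocation, with no added visits, staff or participants. The small downside is that KD meal planning and counselling must fit between the baseline visit and the first delivery, which Section 5 places in the following week.

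Sections 5 and 6 are partly in the past tense, so the trial may already have run. In that case, report the actual order and the time of disclosure as a limitation.

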6. STATISTICAL PLAN

Sample Size. Feasibility and preliminary data for effect size estimation is the primary purpose of this pilot

study (hypothesis generating).

Descriptive analyses.

Demographic, Anthropometric and Baseline Characteristics: Demographic data (i.e., age, education, gender, marital/partner status, employment status, and years since HIV diagnosis) were evaluated using frequencies and reported for each group. Ratio/interval data (i.e., anthropometrics (i.e., height, weight, BMI, waist and hip circumference, cognitive performance by instrument; inflammatory markers (CRP, TNF-a, IFNy, IL-1B, IL-6, IL-8, and IL-12p70); cardiometabolic factors (OGTT, glucose, C-peptide, and insulin) reported via mean/SD at baseline by group. Between-group t-tests will explore group differences at baseline.

Primary analysis: All the primary outcomes (impairment score, inflammatory markers and cardiometabolic factors) will be examined by an analysis of covariance (ANCOVA) including the change from baseline to completion of diet treatment as dependent variable, study group as independent variable, and baseline measures as a covariate, to evaluate the effects of a 12 week KD versus PCD. The lasting cognitive effects of a 12-week KD versus PCD six weeks post intervention completion was determined by an ANCOVA including the change of impairment score from 12 week to 18 week as dependent variable, study group as independent variable, and impairment score at 12 weeks as a covariate.

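### The week-18 analysis is read as a lasting effect after the diet has ended, but the plan neither states nor records what either arm eats from week 12 to week 18

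*Combined protocol and SAP*

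**What the plan says.** Section 2 introduces its primary list with "Compare the impact of a 12-week KD versus PCD on", and the fourth item, 2.1.4, is "Persistence of cognitive effects" at 18 weeks. Section 6 supplies the interpretation: "The lasting cognitive effects of a 12-week KD versus PCD six weeks post intervention completion". The model is an ANCOVA with this specification: "change of impairment score from 12 week to 18 week as dependent variable, study group as independent variable, and impairment score at 12 weeks", the last of these being the covariate. It has no term for diet after week 12.

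On measurement, Section 5 sets data collection at baseline "and week 12 unless otherwise stated". The only item extended further is the cognitive battery: "Cognitive assessments completed at baseline, week 12, and week 18". Section 7 places the two blood draws at baseline and week 12, and the scheduled adverse-effect inquiries at weeks 4, 8 and 12.

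On diet, Section 5 says that all KD meals and snacks are supplied and that "KD group participants also provided nutritional counseling specific to the KD as well as provided with handouts". Delivery starts in the week after baseline and keeps to one weekday throughout the study, with no end week given. No readable sentence says what either arm eats between weeks 12 and 18.

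**The concern.** A claim that an effect lasts beyond a diet needs participants to have stopped the diet, or at least needs a record of who did. The plan has neither. KD participants have been taught the diet and hold written material on it, so some could follow it unaided, and nothing prevents a PCD participant from taking it up.

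A favourable week-18 result then has two readings that point in opposite directions for a later trial. Either the benefit survives stopping, or it needs continued KD and some participants continued. An unfavourable result is also unclear, because it could reflect fading in the KD arm or uptake of KD in the PCD arm.

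This gap is separate from adherence during weeks 1 to 12. Perfect adherence data up to week 12 would not show whether week 18 was off-diet.

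**Working it through.** The plan gives no effect size, SD, continuation rate or week-12-to-18 correlation, so there is no figure of its own to reproduce. The check has two parts.

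**1. Is exposure after week 12 defined or recorded?**
- Defined: Sections 2 and 6 call the diet a 12-week KD, and Section 6 treats week 12 as the end of diet treatment. An end at week 12 is therefore implied. It is not stated for meals, and Section 5 leaves the end of delivery open.
- Recorded: at week 18 there is the cognitive battery and nothing else. No food record, dietary recall or ketone measure is described at any visit.

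**2. What does the planned model return if some participants continue?**

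Notation, with positive values favouring KD:
- d12 is the true KD-minus-PCD effect at week 12.
- r is the fraction of d12 retained after truly stopping.
- f is the fraction of the 7 KD participants (Section 5) who continue.
- b is the within-arm slope of week-18 score on week-12 score.

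All four are assumed, because the documents give none of them.

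The expected week-18 difference is R × d12, with R = r + f(1 − r). The difference in 12-to-18-week change is (R − 1) × d12. The slope of change on week-12 score is (b − 1), and the arms differ by d12 at week 12. The adjusted group coefficient is therefore

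(R − 1)d12 − (b − 1)d12 = (R − b) × d12.

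With no true retention (r = 0), R = f and the coefficient is (f − b) × d12. In units of d12:

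| KD participants continuing | b = 0.5 | b = 1 |
|---|---|---|
| 0 of 7 | −0.50 | −1.00 |
| 1 of 7 | −0.36 | −0.86 |
| 2 of 7 | −0.21 | −0.71 |
| 3 of 7 | −0.07 | −0.57 |
| 4 of 7 | +0.07 | −0.43 |
| 7 of 7 | +0.50 | 0.00 |

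The true off-diet effect is nil in every row. Continuation moves the contrast from a loss toward zero and, once f exceeds b, past it.

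The data also cannot separate r from f, because only R enters the coefficient. R = 1 arises from full retention with nobody continuing (r = 1, f = 0) and from no retention with everybody continuing (r = 0, f = 1). R = 4/7 arises from r = 0 with 4 of 7 continuing, and from r = 0.25 with 3 of 7 continuing: 0.25 + (3/7)(0.75) = 0.57.

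Uptake of KD in the PCD arm acts the other way. If a fraction g adopts it and gains the full effect by week 18 (assumed), the coefficient becomes (R − g − b) × d12, which looks like loss.

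Power shows how easily a loss could be missed. Take d12 = 0.8 SD, r = 0, b = 1, two-sided alpha 0.05, 7 per arm and 14 − 3 = 11 df, all beyond the arm sizes being assumptions. The expected loss is 0.8(1 − f) SD: 0.80 with nobody continuing (power 28%), 0.34 with 4 of 7 continuing (9%), and 0 with 7 of 7 (5%, the alpha level). These figures ignore the extra variance from adjusting for a week-12 score that differs between arms.

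**The case against.** The strongest reply is that the comparison is valid as it stands. Comparing the arms as randomised at week 18 estimates the effect of having been assigned a 12-week KD programme, whatever was eaten later. That is correct, and it is a reasonable quantity to report. However, the plan does not define it so, and its wording about lasting effects after completion describes an off-diet effect.

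A second reply is that this is a hypothesis-generating pilot with 7 per arm, and that one self-reported item will not settle the question. That limits how much weight the point can carry. It does not remove it: Section 6 gives effect-size estimation as a purpose, and a larger sample would not resolve unknown exposure.

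A third is that Section 6 uses the past tense for the week-18 analysis, so collection may be over. The tenses are mixed and the documents do not settle this. The fix therefore needs a fallback.

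Some stronger readings are tempting but unsupported:
- A reader might infer that ongoing treatment will be reported as a lasting effect. That depends on participants continuing, and the documents give no rate.
- A reader might infer that, with 1 to 4 of 7 continuing and no retention, 14% to 57% of the week-12 effect (1/7 to 4/7) would be reported as lasting. Those are raw week-18 differences, which the plan does not compute. Its ANCOVA would mostly show a loss in these cases, reduced by continuation.
- A reader might infer that supplied meals stop at week 12, or that objective 2.1.4 itself refers to six weeks off the intervention. The first is only implied. The second comes from Section 6, since 2.1.4 says only 18 weeks.

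**Conclusion.** The concern holds in limited form. The plan reads week 18 as an effect outlasting the diet, yet it neither states nor records diet after week 12, so it cannot tell persistence from continued treatment. Under the planned model, continued KD pulls the contrast toward zero and so masks loss of benefit. It does not manufacture a positive effect of known size.

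The amount of masking is f × d12 when retention is nil: nothing if nobody continues, and 0.57 × d12 if 4 of 7 do. Where that leaves the contrast depends on b, assumed here to lie between 0.5 and 1. Whether any masking occurs is unknown from the documents, and without a record it could be neither confirmed, excluded nor adjusted for.

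The point affects the interpretation of one of the four listed primary items. It does not touch the week-12 comparisons, and it does not make the randomised week-18 comparison invalid. The change should be made, because it is cheap and alters what can be concluded. The absence of a rule or record is judged on the readable text, since figures are missing from it.

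**What to change.** 1. At the existing week-18 visit, ask both arms one short structured question: was KD (< 50 g CHO/day) followed since week 12, and for how many of the six weeks?
2. In Section 6, define the week-18 result as the effect of assignment to a 12-week KD programme regardless of later diet.
3. Report continuation or uptake by arm, and show week-18 scores by continuation descriptively only. Note that the split is self-selected and small: participants who felt a benefit may be likelier to continue.
4. Do not describe the result as persistence after stopping unless the records show that KD participants were off KD. A rule that most had stopped would be too weak: 3 of 7 continuing leaves 3/7 = 43% of the week-12 difference in the raw week-18 comparison with no retention at all.
5. If week-18 collection is already complete, report the result as an assignment effect with later diet unknown, and drop the word *lasting*.

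The investigators should also state what applies to diet and food delivery after week 12; that choice is theirs.

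The cost is one questionnaire item at a visit that already takes place and a few lines in Section 6. The drawback is that self-reported intake is imprecise, so the item will inform the interpretation without settling it.

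### The only week-18 analysis adjusts for the post-treatment week-12 score, so it does not estimate the diet difference remaining at week 18

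*Combined protocol and SAP*

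**What the plan says.** Objective 2.1.4 in Section 2, listed under the primary comparisons of KD with PCD, is "Persistence of cognitive effects" at 18 weeks. Section 6 (Primary analysis) gives the matching analysis. Its target is "The lasting cognitive effects of a 12-week KD versus PCD six weeks post intervention completion", and the method is an ANCOVA with "change of impairment score from 12 week to 18 week as dependent variable, study group as independent variable, and impairment score at 12 weeks" as the covariate.

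The 12-week outcomes in the same paragraph are handled differently, with "the change from baseline to completion of diet treatment as dependent variable, study group as independent variable, and baseline measures as a covariate". That model stops at the end of the diet, and the descriptive summaries are of baseline data. No other analysis of the week-18 scores is described.

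Section 5 states: "Cognitive assessments completed at baseline, week 12, and week 18". Under Sample Size, Section 6 states: "Feasibility and preliminary data for effect size estimation is the primary purpose of this pilot".

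**The concern.** The objective asks what difference between the diets is still present six weeks after they end. The planned model asks something else: whether KD and PCD participants who had the same score at the end of treatment differ at week 18. If KD works, a KD participant and a PCD participant with equal week-12 scores are not alike in other respects, because one reached that score with the help of the diet. Conditioning on a score that treatment can change gives up the comparison that randomisation protects, and it removes part of the effect being sought.

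The pilot is meant to supply effect sizes. The persistence estimate it passes on could understate a lasting benefit, or show a KD disadvantage where a benefit has simply worn off.

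**Working it through.** The plan states no power, alpha or effect size for this analysis, so there is no figure to reproduce. The check is algebra, followed by simulation under stated assumptions.

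**Inputs from the documents.** The two ANCOVA specifications (Section 6); 7 participants per group (Section 5); cognitive testing at all three times (Section 5).

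**Assumptions, not in the documents.** Equal (unit) SDs, normal scores, two-sided 0.05, benefit scored positive, and values of b and d12 over a range. The only reliability stated is 0.80 to 0.90, for Trails A. It does not fix b for the impairment score.

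**Step 1: what the coefficient is.** The planned model is Y18 − Y12 = a + g·group + c·Y12. The within-group slope of the change on Y12 is c = b − 1. Hence

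g = (d18 − d12) − (b − 1)·d12 = d18 − b·d12.

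This is exact within any dataset when d12 and d18 are the raw group mean differences and b is the pooled within-group slope. In one simulated dataset of 7 per arm, the planned coefficient was 0.1367 and d18 − b·d12 was 0.1367. Regressing Y18 itself on group and Y12 also gave 0.1367, so the change-score form makes no difference. The covariate is what matters.

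**Step 2: what follows.**
- Effect fully kept (d18 = d12): g = (1 − b)·d12.
- Fraction b kept (d18 = b·d12): g = 0.
- Effect fully lost (d18 = 0): g = −b·d12, which has the opposite sign to the week-12 effect at any b above zero.
- In every case g misses d18 by −b·d12.

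**Step 3: size with 7 per arm and d12 = 1 SD** (40,000 simulated trials per scenario). For example, at b = 0.8: kept, 1 − 0.8×1 = +0.20; lost, 0 − 0.8×1 = −0.80.

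| b | Coefficient, kept / lost | Rejection, kept / lost | Planned 95% CI covers d18 |
|---|---|---|---|
| 0.3 | +0.70 / −0.30 | 19% / 8% | 93% |
| 0.5 | +0.50 / −0.50 | 13% / 14% | 86% |
| 0.8 | +0.20 / −0.80 | 8% / 50% | 51% |
| 0.9 | +0.10 / −0.90 | 6% / 84% | 17% |

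When the retained fraction equals b, the mean coefficient is 0.00 and rejection is about 5% at every b.

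**Step 4: a smaller effect, d12 = 0.5 SD.** Coverage at the same four values of b is 94%, 93%, 81% and 63%. At b = 0.8 the coefficients are 0.5 − 0.8×0.5 = +0.10 (kept) and −0.8×0.5 = −0.40 (lost), with rejection 6% and 19%.

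**Step 5: the baseline-adjusted alternative.** Regressing the baseline-to-week-18 change on group and baseline score recovers d18 in every scenario (means 1.00 and 0.00 for true values of 1 and 0), with 95% coverage. Baseline correlations of 0.3, 0.5, 0.7 and 0.7 were assumed alongside the four values of b. Power for a fully lasting effect was then 41% to 63% at 1 SD and 14% to 21% at 0.5 SD. That range reflects the baseline correlation, not b: with b held at 0.8 and d12 = 1 SD, correlations of 0.3, 0.5 and 0.7 give 41%, 48% and 62%.

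A separate simulation with d12 = −0.8 SD (lower scores better), all correlations 0.7 and 4,000 runs agreed. The theoretical planned coefficients for an effect fully kept, 70% kept and gone are −0.24, 0.00 and +0.56, and the simulated means lay within about 0.02 of them. The baseline-adjusted means were −0.80, −0.56 and 0.01, against true values of −0.80, −0.56 and 0.

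**The case against.** The strongest reply is that persistence is never defined as an estimand. On a two-step reading, the 12-week ANCOVA estimates the effect at the end of the diet and the 12-to-18-week model asks whether the arms then move apart. Scoring that second model on its coverage of d18 would hold it to a target it did not have. It is true that the estimand is undefined. But Section 6 presents the model as giving the KD versus PCD effect six weeks after the intervention. Nor does the coefficient give the simple further change, d18 − d12, unless b = 1 or d12 = 0. The 12-week result helps tell no effect at any time from an effect retained, but the plan gives no way to combine the two models into a week-18 difference with an interval.

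The plan also states no significance rule, so the rejection rates above describe a 0.05 test that the documents do not specify. That stands, and the coefficients and their bias do not depend on it. It does not rescue the further-change reading either: no margin for maintenance is stated, and a non-significant result with 7 per arm shows neither maintenance nor absence of a lasting effect.

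The size of the error is unknown. With d12 = 0.5 SD and b of 0.3 to 0.5, coverage is close to nominal. The worst figures need a 1 SD effect and b of 0.8 to 0.9. This stands.

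Finally, the better model will not be precise: its 95% interval averages about 1.7 to 2.3 SD wide under these assumptions. That also stands. The gain is a correctly aimed estimate and interval, not a powered test.

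**Conclusion.** The concern holds and should be fixed. The algebra is certain and needs no assumed values: the planned coefficient is d18 − b·d12, which is not the week-18 difference unless b or d12 is zero. A listed primary objective therefore has no analysis that estimates it.

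The practical size is conditional on b and d12, which the documents do not give. Over the assumed range, coverage of the true week-18 difference runs from 94% (d12 = 0.5 SD, b = 0.3) down to 17% (d12 = 1 SD, b = 0.9). At b = 0.5 a fully lasting and a fully lost benefit give coefficients of equal size and opposite sign. Above 0.5 the lost benefit gives the larger coefficient, and below 0.5 the lasting one does.

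**What to change.** Replace the 18-week sentence in Section 6 with:

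> Persistence will be assessed by ANCOVA of the change in impairment score from baseline to week 18, with study group and baseline impairment score in the model. The week-18 KD−PCD difference will be reported beside the week-12 difference, each with a 95% confidence interval.

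One repeated-measures model for weeks 12 and 18, adjusted for baseline and with a week-18 contrast, is an acceptable alternative. The week 12-to-18 change can stay as a descriptive summary by arm.

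Section 6 describes this analysis in the past tense. If it has already been run, report it as planned and give the baseline-adjusted result as a labelled added analysis.

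The cost is one or two sentences, or one added analysis. The three cognitive assessments are already scheduled, so no new data are needed.
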